5.1 Protocol requested treatment

5.1.1 Investigational treatment

The sponsor will provide the following study medications:

- 50 mg LCZ696 film-coated tablet that contains 24 mg sacubitril and 26 mg valsartan (as sacubitril valsartan sodium salt complex).
- 100 mg LCZ696 film-coated tablet that contains 49 mg sacubitril and 51 mg valsartan (as sacubitril valsartan sodium salt complex).
- 200 mg LCZ696 film-coated tablet that contains 97 mg sacubitril and 103 mg valsartan (as sacubitril valsartan sodium salt complex).

Patients will be required to take the study medication twice daily in addition to their daily therapies, possibly at 12 hour interval (i.e., at 7:00 in the morning and 19:00 in the evening). Tablets should be taken with a glass of water, and may be administered with or without food.

5.1.2 Additional study treatment

No additional treatment beyond investigational treatment is requested for this trial.

5.2 Treatment groups

Patients will be assigned in a ratio of 1:1 within each stratum to one of the following treatment groups

- **Pre-discharge** initiation of LCZ696 treatment, where treatment is started prior to Discharge (see study design for timing);
- **Post-discharge** initiation of LCZ696 treatment, where treatment should be started AFTER Discharge but within two (2) weeks after Discharge (see study design for timing).

5.3 Treatment assignment, randomization

Stratification will occur *prior to* Randomization and it will be based on the patient's HF-therapy prior to admission (i.e., ACEI, ARBs, or 'ACEI/ARB-inhibition-naïve treatment'). Stratification will ensure that within a stratum the distribution between Pre- and Post-discharge is similar. It is expected that the naïve patients will represent *at least* 7% of the total number of patients (i.e., 70 patients from in total 1000 randomized patients).

For the samples size of 1000 patients, a maximum of 930 of ACEI or ARB-treated patients will be randomized, to ensure achieving the minimum target of 70 ACEI/ARB-naïve patients. However, more than 70 RAAS inhibition-naïve treatment patients could be included if during the study conduct a higher number is enrolled. Stratification will be performed at the country level.

Randomization/treatment assignment will be accomplished through the Interactive Response Technology (IRT).

5.4 Treatment blinding

This is an open-label study, therefore, after randomization, the investigator, pharmacist and subject will be aware of which treatment is administered to the subject. If the investigator interacts with the Novartis clinical team, he/she should not disclose treatment assignment to the Novartis team, where avoidable. The independent statistician, programmer and data manager coordinator, who need to be unblinded to review interim analysis reports for the DMCs, will not be involved in any other trial activities. Due to the nature of the CRF, accidental systematic unblinding is possible for anyone involved in ongoing data review. However, as treatment assignment is not openly apparent, and it would need a combination of data from different panels to ascertain, it is assumed that the scientific credibility of the study will not be compromised.

5.5 Treating the patient

5.5.1 Patient numbering

Each patient is uniquely identified in the study by a combination of his/her center number and patient number. The center number is assigned by Novartis to the investigative site. Upon signing the informed consent form, the patient is assigned a patient number by the investigator. At each site, the first patient is assigned patient number 1, and subsequent patients are assigned consecutive numbers (e.g. the second patient is assigned patient number 2, the third patient is assigned patient number 3). The investigator or his/her staff will contact the IRT and provide the requested identifying information for the patient to register them into the IRT.

For this study using eCRFs, only the assigned patient number should be entered in the field labeled "Patient ID" on the EDC data entry screen (e.g. enter '1', '2', etc.). Once assigned to a patient, the patient number will not be reused. If the patient fails to be randomized for any reason, the IRT must be notified within 2 days that the patient was not randomized. The

reason for not being randomized will be enter on Screening phase disposition electronic Case report form (eCRF).

The following eCRF must be completed for **subjects who screen fail**: The demography eCRF, Informed consent eCRF; Inclusion/ Exclusion eCRF; the adverse event eCRF paper serious adverse event (SAE) form should be complete for any SAE that occurred during the screening period; Death eCRF (only in case of death during the screening period) and Withdrawal of informed consent eCRF (if consent was withdrawn during the screening period before the patient was randomized).

5.5.2 Dispensing the investigational treatment

Each study site will be supplied by Novartis with investigational treatment. The investigational treatment packaging has a 2-part label. A unique medication number is printed on each part of this label which corresponds to one of the two treatment groups and a dose level. Investigator staff will identify the investigational treatment package(s) to dispense to the patient by contacting the IRT and obtaining the medication number(s). Immediately before dispensing the package to the patient, investigator staff will detach the outer part of the label from the packaging and affix it to the source document (Drug Label Form) for that patient's unique subject number.

5.5.3 Handling of study treatment

5.5.3.1 Handling of investigational treatment

Investigational treatment must be received by a designated person at the study site, handled and stored safely and properly, and kept in a secured location to which only the investigator and designees have access. Upon receipt, all investigational treatment should be stored according to the instructions specified on the labels. Clinical supplies are to be dispensed only in accordance with the protocol. Technical complaints are to be reported to the respective Novartis CPO Quality Assurance.

Medication labels will comply with the legal requirements of each country. They will include storage conditions for the investigational treatment but no information about the patient except for the medication number.

The investigator must maintain an accurate record of the shipment and dispensing of investigational treatment in a drug accountability log. Monitoring of drug accountability will be performed by monitors during site visits or remotely and at the completion of the trial. Patients will be asked to return all unused investigational treatment and packaging at the end of the study or at the time of discontinuation of investigational treatment.

At the conclusion of the study, and as appropriate during the course of the study, the investigator will return all unused investigational treatment, packaging, drug labels, and a copy of the completed drug accountability log to the Novartis monitor or to the Novartis address provided in the investigator folder at each site.

5.5.3.2 Handling of other study treatment

Not applicable.

5.5.4 Instructions for prescribing and taking study treatment

The target dose of LCZ696 is 200 mg twice daily.

The recommended starting dose of LCZ696 is 100 mg twice daily.

A starting dose of 50 mg LCZ696 twice daily should be considered for:

- (1) patients not currently taking an angiotensin-converting enzyme (ACE) inhibitor or an angiotensin II receptor blocker (ARB);
- (2) patients previously taking low doses of these agents;
- (3) patients with moderate hepatic impairment (Child Pugh B classification), or with AST/ALT values more than twice the upper limit of the normal range;
- (4) patients with moderate renal impairment (eGFR 30-60 ml/min/1.73 m²).

The dose of LCZ696 should be doubled every 2-4 weeks to achieve the target dose of 200 mg twice daily, as tolerated by the patient.

If a dose of LZC696 is missed, the patient should take the next dose at the scheduled time.

Investigator judgment will be the basis for up-titration toward the target dose taking into consideration tolerability (i.e., incidence of hypotension, renal or hepatic impairment and hyperkalemia) based on clinical evaluation and laboratory assessment. In case of patients experiencing tolerability issues, the investigator should consider (a) adjusting concomitant medications, or (b) temporary down–titration, or (c) temporary or permanent discontinuation of LCZ696.

All therapy dosages prescribed and dispensed to the patient and all dose changes during the study must be recorded on the Dosage Administration Record CRF. Similarly, if any adverse events is reported, the appropriate eCRF page must be completed.

All kits of investigational treatment assigned by the IRT will be recorded in the IRT system.

The investigator should promote compliance by instructing the patient to take the study treatment exactly as prescribed and by stating that compliance is necessary for the patient's safety and the validity of the study. The patient should be instructed to contact the investigator if he/she is unable for any reason to take the LCZ696 as prescribed.

5.5.5 Permitted dose adjustments and interruptions of study treatment

At the discretion of the investigator, patients could be initiated and may be maintained on either 50 or 100 mg LCZ696 bid, if they are unable to tolerate up-titration to higher doses of LCZ696 in this open-label study.

Every attempt should be made to achieve and maintain patients on the target LCZ696 dose level of 200 mg bid.

Study drug dose level adjustments should be based on overall safety and tolerability with special focus on:

- a) hyperkalemia (Appendix 3: treatment guidelines for hyperkalemia);
- b) symptomatic hypotension (Appendix 4: guidelines for management of BP);
- c) clinically significant decrease in eGFR/increase in serum creatinine (Appendix 5: guidelines for management of renal dysfunction).
- d) worsening hepatic function. (Appendix 2: Liver event and laboratory trigger definitions and follow up requirements).

If, in the opinion of the investigator, the patient does not tolerate the assigned dose level, the investigator should consider the following:

- 1. Whether non-disease-modifying medication (e.g., diuretics, nitrates, CCBs, α -blockers) can be reduced to rectify the situation, before reducing the dose of the study drug to a lower dose level (100 mg bid or 50 mg bid LCZ696).
- 2. Adjust doses of disease-modifying medications (e.g., β -blockers, aldosterone antagonists) if it is believed that they are the most likely cause of the adverse effect.
- 3. If adjustment/elimination of concomitant medications is not possible or does not alleviate the side effects of concern, the investigator may down-titrate the dose of the LCZ696 to:
 - a. the next lower level
 - The patient should be re-challenged with a higher dose when the investigator feels it is appropriate to do so per the directions provided below in this section.
 - b. temporary or permanent withdrawal of the study drug

 If the study drug is temporarily discontinued, it should be reintroduced as soon as medically justified in the opinion of the investigator.

Any changes in the LCZ696 dose level must be recorded on the Dosage Administration Record eCRF and registered in the IRT system. Similarly, if any adverse events is reported, the appropriate (AEV) eCRF page must be completed.

Adjustment of LCZ696 dose level

If, adjustment of concomitant medications as per the guidance provided above does not rectify the situation, the investigator may consider adjusting the dose of LCZ696 according to the following instructions.

If down-titration is necessary, the patient should be down-titrated to the next lower dose level. The patient may continue to receive the lower dose level for a recommended period of 1 to 4 weeks, or longer based on the investigator's judgment, before re-challenging the patient with the next higher dose level. For example, a patient who encounters tolerability problems at the target dose of 200 mg LCZ696 bid could be down-titrated to the dose of 100 mg LCZ696 bid for 1 to 4 weeks.

If the tolerability issues are not alleviated despite down-titration by one dose level, the investigator may lower the study drug dose further to the next lower level for 1 to 4 weeks, if feasible, or to temporary discontinue the study drug (see next paragraph for details).

In some instances, according to the safety and tolerability criteria and the investigator's judgment, LCZ696 dose level of 50 or 100 mg bid can be maintained if he/she considers that

the patient's condition would not allow any further up-titration to the target dose of 200 mg LCZ696 bid. In this case it would be acceptable to maintain the patient at the highest tolerated dose level.

At each up- or down-titration, IRT should be contacted to register any changes in the patient's LCZ696 dose level, including cases of temporary and permanent withdrawal of the study drug, and to obtain the medication numbers of the LCZ696 supplies required for the new dose level.

Study drug restart after temporary treatment interruption

Once the investigator considers the patient's condition appropriate for receiving LCZ696, the investigator should re-start the patient on the study drug at the most appropriate and allowable dose level per his/her medical judgment. If tolerated, the dose of LCZ696 should be doubled every 2 to 4 weeks to the target dose of 200 mg twice daily, as tolerated by the patient and as per the investigator's judgment.

Should the patient not tolerate the re-started study drug at a particular dose level, he/she may be down-titrated again (if appropriate) or the study medication temporary discontinued again and a new attempt to up-titrate or reintroduce the study drug could be considered by the investigator if justified in his/her medical judgment.

Study visits should occur as close as possible to the time points indicated in the Assessment Schedule. The time interval between the regular visits should be maintained as scheduled, irrespective of the number of unscheduled visits that may be performed in between, according to the visit and time schedule described in the Assessment Table.

In case of pregnancy discovered during the study, the patient should be instructed to stop taking the study drug immediately. See Section 7.7 for further details on pregnancies and reporting guidelines.

Upon permanent discontinuation of LCZ696 treatment, a minimum of 36 h between last dose LCZ696 and first dose of ACEI should be completed. Any changes in the study drug dose level, including temporary/permanent withdrawal or re-start of the study drug, must be recorded on the Dosage Administration Record eCRF and registered in the IRT system.

5.5.6 Rescue medication

Guidance on handling liver event, hyperkalemia, hypotension, and renal dysfunction are provided to investigators in Appendix 2, 3, 4, and 5, respectively. Based on reported tolerability events, changes/lowering in LCZ696 dose levels or temporary discontinuation are allowed during the study and must be recorded in the eCRF page.

In case of concomitant medication administration, please record them in the appropriate eCRF page, and in the occurrence of an adverse event refer to the safety section of this protocol for reporting procedures.

ONLY if LCZ696 has been permanently discontinued, patients may resume the ACEIs and/or ARBs treatment. Se Section 5.5.9 for discontinuation of study treatment.

5.5.7 Concomitant treatment

The investigator should instruct the patient to notify the study site about any new medications he/she takes **after the patient was enrolled into the study**. All medications, procedures and significant non-drug therapies (including physical therapy and blood transfusions) administered after the patient was enrolled (i.e., after signing ICF) into the study must be recorded in the CRFs.

Medication to be recorded in the CRFs:

- Prior medications: Medications taken BEFORE hospital admission will be reported in the CRFs (also needed for stratification).
- Treatment administered **after signing ICF** will be recorded in the CRFs.

Medications administered during the acute treatments of the decompensated heart failure event (from admission to the time of signing ICF) will NOT be included in the CRFs but will remain as source documentation.

5.5.7.1 Heart failure medications for chronic therapy and other cardiovascular medications

Patients should be on an optimal medical regimen of HF medications except ACE inhibitors and ARBs during the whole study duration. The use of an MRA and a β-blocker (if tolerated) should be considered in all patients eligible for this study. In self-identified black patients, the use of isosorbide dinitrate/hydralazine hydrochloride (e.g., BiDil®) should be considered. Every effort should be made to keep the dose level of these background HF medications stable throughout the entire study. However, if the patient's condition warrants a change in any of these medications (for example, if the investigator believes a medication is causing an adverse event), it is allowed at the discretion of the study investigator.

Diuretics may be used and may be adjusted throughout the length of the study at the discretion of the investigator.

5.5.7.2 Medications known to raise potassium levels

Concomitant use of potassium-sparing diuretics (triamterene, amiloride), mineralocorticoid antagonists (e.g. spironolactone, eplerenone), potassium supplements, and salt substitutes containing potassium or other agents (such as heparin) may lead to increases in serum potassium, and to increases in serum creatinine.

Medications known to raise potassium levels should be used with caution while the patient is receiving the study medication due to the increased possibility of occurrence of hyperkalemia. The investigator is encouraged to assess patients' potassium levels regularly, especially if LCZ696 is co-administered with these agents.

5.5.7.3 Phosphodiesterase-5 (PDE-5) inhibitors

PDE-5 inhibitors (e.g., sildenafil, vardenafil and tadalafil) should be used with caution while the patient is receiving LCZ696 due to the increased possibility of occurrence of hypotension.

5.5.7.4 Intravenous neseritide, nitroprusside and nitrates

The concomitant administration of LCZ696 with intravenous (i.v.) **nitrates/nitroglycerin** has been studied in healthy volunteers. There was no significant difference in the magnitude, dose or time-course of the decrease in systolic and diastolic blood pressure when nitroglycerin was given alone compared to the co-administration of nitroglycerin and LCZ696.

The concomitant administration of LCZ696 with i.v. **neseritide or nitroprusside** has **not** been studied. In the event a study patient requires the concomitant administration of neseritide and/or nitroprusside with LCZ696, the investigator should consider starting them at a lower dose or a slower infusion rate while monitoring the patient's blood pressure carefully.

5.5.7.5 Atorvastatin and other statins

In vitro data indicates that sacubitril inhibits OATP1B1 and OATP1B3 transporters. LCZ696 may therefore increase the systemic exposure of OATP1B1 and OATP1B3 substrates such as statins.

In vivo, at steady state, the levels of atorvastatin increased when co-administered with LCZ696. Co-administration of LCZ696 increased the Cmax of atorvastatin and its metabolites by up to 2-fold and AUC by up to 1.3-fold. Therefore, caution should be exercised upon co-administration of LCZ696 with statins.

However, steady state pharmacokinetics of LBQ657 (neprilysin component of LCZ696) were not changed, valsartan levels decreased slightly when administered with atorvastatin. The effect of LCZ696 on other statins has not been examined.

Based on these results, caution is recommended when LCZ696 is co-administered with atorvastatin or other statins that are substrates of the organic anion transporters, OATP1B1 and OATP1B3.

5.5.8 Prohibited treatment

ACEIs, ARBs and direct renin inhibitors such as aliskiren

In this clinical trial, patients' pre-study ACEIs/ARBs will be replaced with LCZ696.

Due to the potential risk of angioedema when used concomitantly with an ACE inhibitor, LCZ696 must not be started for at least 36 hours after discontinuing ACE inhibitor therapy.

LCZ696 should not be co-administered with an ARB due to the angiotensin II receptor blocking activity of valsartan.

The concomitant use of any ACEIs or ARBs is strictly prohibited while the patient is receiving LCZ696. If the investigator believes that addition of an ACEI or ARB is necessary, then LCZ696 must be discontinued. If treatment with LCZ696 is stopped, ACE inhibitor therapy must not be initiated until 36 hours after the last dose of LCZ696.

Concomitant administration of direct renin inhibitors, such as aliskiren is also prohibited in this study.

Other medications

Bile acid sequestering agents, such as cholestyramine and colestipol are **prohibited** to avoid interference with study drug absorption.

5.5.9 Discontinuation of study treatment

During the **Treatment Epoch** (up to 10 weeks after Randomization), *permanent* discontinuation of LCZ696 treatment should NOT be considered withdrawn from the study. The patient should return for the assessments indicated for Visit 199 (10-weeks after Randomization), if discontinued before that visit, and Visit 199 will be also the End of Study visit for that patient. If they fail to return for these assessments for unknown reasons, every effort (*e.g.* telephone, e-mail, letter) should be made to contact them as specified in Section 5.5.11.

During the **Follow-up Epoch**, *permanent* discontinuation of LCZ696 constitutes withdrawal from the study. Under these circumstances, the patient should be evaluated at a final study visit but will not undergo assessments thereafter unless additional follow-up is required due to prior occurrence of an adverse event.

The investigator must also notify the IRT of the patient's *permanent* discontinuation of LCZ696 and record it on the Drug Administration Record of the eCRFs.

The emergence of the following circumstances will require LCZ696 discontinuation:

- Withdrawal of informed consent
- Failure to follow study-related instructions
- Pregnancy (Section 7.7)
- Use of prohibited treatment
- Investigator thinks that continuation would be detrimental to the patient's well-being

LCZ696 may be permanently discontinued at the investigator's discretion if any of the following occurs:

- Any severe suspected drug-related AE
- Suspected occurrence of angioedema. A patient with any signs or symptoms of clinically significant angioedema should be thoroughly evaluated by the investigator and constitute a reason for discontinuation of study medication.

Depending on the serum potassium, blood pressure, or eGFR, patients may need to have their LCZ696 dose or the dose of another concomitant medication reduced or discontinued, or, if appropriate, have potentially contributing agents adjusted. Please refer to Appendices 3, 4, and 5 for treatment guidelines for hyperkalemia, hypotension, or renal dysfunction, respectively.

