Similarly, a 36 hours washout period will be implemented any time when LCZ696 is discontinued and patients resume the use of an ACEI. This 36-hour ACEI/LCZ696-free washout period is consistent with other LCZ696 studies, as well as the CLCZ696B2314/PARADIGM-HF study (McMurray JJV, 2014a; Solomon SD, 2012).

If angioedema occurs, LCZ696 should be immediately discontinued and appropriate therapy and monitoring should be provided until complete and sustained resolution of signs and symptoms has occurred. LCZ696 must not be re-administered. The occurrence of an angioedema-like event must be reported using the appropriate CRF pages including the narrative of the event.

The risk of angioedema is considered to be adequately managed by exclusion criteria, warnings and precautions that recommend permanent discontinuation of LCZ696 and symptomatic treatment and monitoring in case angioedema occurs.

Other risks

Other risks may be associated with general study procedures, such as pain and infection potentially associated with needle pricks required for blood draws. All of these risks are no different from ones associated with similar studies.

Risks to patients in this trial will be minimized by compliance with the entry criteria, close clinical monitoring.

Benefits of LCZ696

LCZ696 offers an innovative approach to the treatment of patients with heart failure through enhancement of the beneficial effects of the endogenous natriuretic peptides (NP) system and other vasoactive peptides while simultaneously limiting the detrimental effects of RAAS over-activation. It has been shown that treatment with LCZ696 translated into a clinically meaningful benefit over current evidence-based guideline recommended ACEI therapy for reduction in CV death, all-cause mortality, HF hospitalization, including first and total hospitalization, and improvement in symptoms and patient-reported outcomes in patients with NYHA Class II-IV HF with systolic dysfunction (HFrEF) when LCZ696 has been taken for an average of 27 months (McMurray JJ, 2014).

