7.2 Angioedema-like events

Angioedema

Angioedema is a type of abrupt swelling that occurs under the skin and/or mucous membranes and is often localized to the head, neck, throat, and/or tongue, but may occur elsewhere, including the genitalia and intestines. Severe cases may be associated with airway compromise. Although, the mechanism is not fully understood, bradykinin has been implicated as the putative mediator. Therefore, medications that raise the levels of endogenous bradykinin by inhibiting the enzymes responsible for its breakdown, such as ACE, aminopeptidase P, and NEP, may result in this potentially dangerous side effect.

If angioedema occurs, LCZ696 should be immediately discontinued and appropriate therapy and monitoring should be provided until complete and sustained resolution of signs and symptoms has occurred. LCZ696 must not be re-administered. The procedure for reporting angioedema-like events is outlined in Section 8.4 of this document.

In the event of angioedema reporting, the treatment with LCZ696 must be immediately and permanently interrupted (i.e., do not wait for the adjudication outcome).

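### For suspected angioedema, section 5.5.9 gives a looser, discretionary rule than the immediate and permanent stop in section 7.2, and does not point to it

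*Protocol*

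**What the plan says.** Protocol 5.5.9 has two lists. The first names five circumstances in which LCZ696 has to be stopped: withdrawn consent, failure to follow instructions, pregnancy, prohibited treatment, and the investigator's view that continuing would harm the patient. Angioedema is not among them.

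The second list opens with "LCZ696 may be permanently discontinued at the investigator's discretion if any of the following occurs". Its second entry reads "Suspected occurrence of angioedema. A patient with any signs or symptoms of clinically significant angioedema should be thoroughly evaluated by the investigator", and adds that such signs or symptoms "constitute a reason for discontinuation of study medication". For other events 5.5.9 sends the reader elsewhere: to section 7.7 for pregnancy, and then "Please refer to Appendices 3, 4, and 5 for treatment guidelines for hyperkalemia, hypotension, or renal dysfunction, respectively". The angioedema entry has no reference.

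Protocol 7.2, whose title refers to angioedema-like events, calls for immediate discontinuation if angioedema occurs and adds "LCZ696 must not be re-administered". It continues: "The procedure for reporting angioedema-like events is outlined in Section 8.4 of this document". It then gives the strict rule: "In the event of angioedema reporting, the treatment with LCZ696 must be immediately and permanently interrupted (i.e., do not wait for the adjudication outcome".

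Protocol 3.6 repeats the immediate stop and the ban on giving the drug again. It also says "The occurrence of an angioedema-like event must be reported using the appropriate CRF pages including the narrative of the event". Protocol 8.4 has the investigator complete a questionnaire for swelling that looks like angioedema, and has every report sent to the adjudication committee.

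**The concern.** Section 5.5.9 is where an investigator would look for the stopping rules, and section 5.5.6 refers readers there. On suspected angioedema it asks for a thorough evaluation and leaves permanent discontinuation to judgment. The stricter instruction is in a later safety section that 5.5.9 does not mention.

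What is at stake is the safety of an individual patient. Section 7.2 itself notes that severe angioedema can compromise the airway. An investigator who interrupts LCZ696 under 5.5.9 and treats the stop as temporary then falls under the restart paragraph in 5.5.5. That paragraph leaves restarting to medical judgment and makes no exception for angioedema.

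**Working it through.** No arithmetic decides this point, so the check sets the rules side by side.

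| | Section 5.5.9 | Section 7.2 |
|---|---|---|
| Trigger | Suspected angioedema | Angioedema that occurs; angioedema reporting |
| Force | Optional; clinically significant signs are a reason to stop | Obligatory |
| Timing | Not stated | Immediate, before adjudication |
| Permanence | At discretion | Permanent |
| Giving the drug again | Not addressed | Prohibited |
| Link to the other section | None | None |

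**Step 1: do both rules reach the same event?** Section 7.2 does not define angioedema reporting, so this has to be inferred. Four pieces of text support the inference:
- The title of 7.2 covers angioedema-like events.
- Section 7.2 takes its reporting procedure from 8.4.
- Under 8.4, swelling that only looks like angioedema is reported, and all reports are adjudicated. Section 3.6 likewise makes reporting of angioedema-like events compulsory.
- An order not to wait for adjudication has little purpose if the event is already confirmed.

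A suspected event is therefore, most naturally, a reported event, and it falls under both sections.

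**Step 2: can both be obeyed?** Yes. Section 5.5.9 permits permanent discontinuation and forbids nothing that 7.2 demands. An investigator who follows 7.2 also complies with 5.5.9.

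**Step 3: does following 5.5.9 alone satisfy 7.2?** No. Under 5.5.9 the investigator may evaluate the patient and continue, or interrupt and later restart. On the reading in step 1, 7.2 excludes both.

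**Step 4: how many patients?** The documents give no count of suspected or angioedema-like events, or of patients continued or restarted after one. The nearest figure is in 3.6. In the earlier trial against enalapril, angioedema was reported in 19 of 4187 LCZ696 patients during randomized treatment: 19 / 4187 = 0.0045, or 0.45% (printed as 0.5%). Section 1.1 gives that trial a median follow-up of 27 months. The figure is the incidence of reported angioedema, not of harm from this wording. It is context only and is not scaled to this trial.

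**The case against.** The best defence is a two-tier reading: judgment while angioedema is only suspected, and a compulsory stop once the investigator calls it angioedema. The wording gives this some support. The protocol speaks of angioedema-like events when it means the wider class, and the compulsory sentence in 7.2 drops that qualifier. Section 8.4 also says that an angioedema adverse event is recorded only if the criteria of section 7.1 are met, so reporting could mean adverse event reporting.

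The defence can add that the protocol is not silent on safety. The 5.5.9 entry treats clinically significant signs as a reason to stop. The compulsory list in 5.5.9 has a general provision for harm to the patient. Sections 3.6 and 7.2 both ban giving the drug again, and 3.6 counts permanent discontinuation among the precautions. Section 8.4 mentions an investigator manual that is not among the documents and may have settled the matter at sites. The situations that 5.5.5 singles out for dose adjustment are potassium, blood pressure, renal function and liver function, not angioedema.

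Part of this stands. The reach of 7.2 to unconfirmed events is an inference, and confusion at sites is not shown. A reader might infer that the two sections give opposite orders. The documents do not support that: 5.5.9 is a permissive clause beside a stricter one.

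The two-tier reading does not remove the point. It leaves the instruction not to wait for adjudication with little work to do. The softening words in 5.5.9 cover only clinically significant angioedema, and they do not say that the stop is immediate, is permanent, or rules out giving the drug again.

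**Conclusion.** The inconsistency is real and should be corrected. Section 5.5.9 states a looser rule than 7.2 for what is most naturally the same event, and does not direct the reader to the stricter one. A site that follows 7.2 is safe; a site that relies on 5.5.9 alone may not be.

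The conclusion rests on reading angioedema reporting in 7.2 through 8.4, which the text favours but does not state. If the two-tier reading was intended, the protocol does not say so, and the boundary between the tiers is undefined.

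The size in patients cannot be derived. The effect on the endpoints is judged negligible: the wording could change week-10 titration success or discontinuation due to adverse events only for patients whose treatment decision turned on it. That judgment assumes such patients are few, which the documents do not quantify. A reader might take 0.45% as the share of patients exposed to harm, or infer that the trial's results are affected; neither follows.

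**What to change.** Move angioedema from the discretionary to the compulsory list in 5.5.9, with an explicit trigger. Suggested text:

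> Angioedema, including any suspected event for which an angioedema questionnaire is submitted under Section 8.4: discontinue LCZ696 immediately and permanently, without awaiting adjudication, and do not re-administer (see Section 7.2).

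Keep the instruction to evaluate the patient thoroughly, and use the same trigger wording in 7.2 so that reporting is defined once. A bare cross-reference from 5.5.9 to 7.2 would be a smaller change, but would leave the trigger undefined. If the sponsor does want judgment for unconfirmed swelling, 7.2 has to say so. A clause in the 5.5.5 restart paragraph excluding angioedema is optional.

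The cost is small: one entry moved and reworded, one trigger aligned, and no added procedures. Section 11.1 requires a written amendment, so the change can go into the next one; until then sites can be reminded that 7.2 applies. The clinical downside is that some patients with equivocal swelling stop LCZ696 permanently, even if adjudication later finds no angioedema. Section 7.2 on its natural reading already requires this.
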